Figure 10. Macrophage and neovascular endothelial staining of carotid plaque in patients with stroke (unstable plaque) and asymptomatic patients (stable plaque). Dark brown areas in Panel A and B: CD68 staining (macrophage marker); Panels C and D: CD31 staining (endothelial cell marker). 5 μ m sections of carotid plaque were removed during CEA. 18F-flotegatide in unstable plaque (panels A and C) was increased (TBR of 2.18) compared to stable plaque (panels B and D) (TBR 1.57).

TIMELINE (ALL AIMS)

	0-4mo	4-8mo	8-12mo
Optimization of tracer synthesis, PET-MRI and immunohistochemical staining			
SA1 PET-MRI of patients with carotid plaque			
SA2 Histologic studies of plaque			
SA2 Ex-vivo binding studies			
Data Analysis			

FUTURE DIRECTIONS

Our long-term goal is to translate the use of 18F-flotegatide for identification of vulnerable plaque in individuals with carotid atherosclerosis. The R56 bridge award will enable us to optimize PET-MRI of carotid plaque with 18F-flotegatide, demonstrate that 18F-flotegatide uptake in carotid plaque can be imaged with PET-MRI and will establish that flotegatide uptake in carotid plaque is integrin mediated. Results from the studies proposed in this R56 application will be used as preliminary data (demonstrating the feasibility of using 18F-flotegatide for imaging unstable plaque with PET-MRI) in an RO1 application. In the future RO1 application

we propose to test our hypothesis that 18F-flotegatide may be preferentially extracted and retained by carotid artery plaque in patients with clinical symptoms of stroke or TIA (vulnerable plaque) compared to asymptomatic control patients (stable plaque) in a larger cohort of 20 symptomatic patients and 20 asymptomatic controls.

Section 4.0

Trial Design

APPROACH

PET-MR of Carotid Plaque

PET-Protocol:

[figure not shown]
A total of 6 patients (3 with stroke or TIA and 3 asymptomatic) will undergo noninvasive PET-MR imaging (Imaging protocol is described below) after injection of 18F-Flotegatide. Our preliminary studies show that there is maximal plaque to blood pool contrast at 2h after injection of 18F-flotegatide. A dose of 10-12.5 milliCurie (370MBq-462.5MBq) of 18F-flotegatide will be injected intravenously and PET-MR imaging will be performed 2 hours (+/- 30 mins) after injection on a Siemens Biograph mMR (Siemens Healthcare Erlangen, Germany) using a dedicated head and neck coil (Siemens Healthcare). Scout images will be obtained for localization of the carotid arteries. An mMR standard Dixon water-fat MR sequence will be obtained and segmented (into air, lung tissue, soft tissue and fat) for MR-based PET attenuation correction (MR-AC) [54]. PET acquisition will begin with the start of the Dixon MR sequence in the same bed position. PET acquisition time will be 15 min in three-dimensional list mode. The PET data from the PET-MR scan will be reconstructed using ordered-subsets expectation maximization iterative reconstruction algorithm (OSEM 3D) (6 iterations, 21 subsets, zoom 2.0) with MR based attenuation correction yielding 512 x 512 image slices (voxel size: 0.70 x 0.70 x 2.03 mm). Attenuation maps for correction of the PET data from the PET-MR scanner will be generated on the basis of the Dixon water-fat MR sequence using the postprocessing software of the scanner. Once plaque is localized on the MR images, the corresponding coregistered PET image will be visually evaluated for 18F-flotegatide uptake. The region corresponding to the plaque on the PET image will be analyzed with commercially available software (MIM) to quantify standard uptake value (SUV) and TBR of 18F-flotegatide. MRI of plaque will be examined for markers of vulnerability including, fibrous cap, lipid rich necrotic core and intraplaque hemorrhage.

MRI-MRA for visualization and co-registration of atherosclerotic plaque:

The MRI protocol will consist of high- spatial resolution 3D imaging sequences in order to detect major vulnerable plaque features and minimize partial volume effects due to tortuous carotid arteries. The sequences will be: a) 3D MP-RAGE -a heavily T1- weighted imaging sequence for detection of intraplaque hemorrhage; b) 3D time-of-flight (TOF) for definition of luminal stenosis; and c) pre- and post-contrast T1-weighted 3D turbo spin echo (SPACE) to detect and quantify the lipid-rich necrotic core and fibrous cap. This will be followed by contrast injection (Gadolinium- DTPA, single dose 0.1 mmol/kg bodyweight, injection rate 2-3 cc/sec). Post-contrast SPACE will be acquired 5 minutes post injection. In addition, contrast-enhanced MRA may also be added into the protocol to obtain high- quality MRA. Typical imaging parameters are: 3D MP-RAGE axial acquisition, TR/TE = 15/3.5 msec, FOV = 160x160 mm², resolution = 0.6x0.6 mm², slice = 2 mm interpolated to 1 mm, flip angle = 15°, inversion time = 500 msec, turbo factor = 30. 3D TOF axial acquisition, TR/TE = 20/4.6 msec,

FOV = 160x160 mm², resolution = 0.6x0.6 mm², slice = 2 mm interpolated to 1 mm, flip angle = 20°. 3D SPACE coronal acquisition, TR/TE = 100/15 msec, FOV = 160x160 mm², resolution = 0.6x0.6 mm², slice = 0.6 mm, echo train = 50. Image quality review, processing (multi-planar reconstruction, MPR), and tissue characterization (outlining and size quantification) will be conducted on an image workstation with FDA-approved carotid plaque analysis software, MRI-Plaqueview (VPDiagnostics, Seattle, WA). From each of 3D sequences, contiguous cross-sectional slices that are perpendicular to the common carotid artery will be reconstructed. Intraplaque hemorrhage will be identified on 3D MP-RAGE as a hyper-intense area. Lipid rich necrotic core and fibrous cap will be identified on post-contrast 3D SPACE as hypo-intense and hyper-intense areas, respectively, with pre- contrast SPACE as reference. Vessel wall, lumen, and individual components will be outlined in a semi- automatic fashion. Their volumes will then be reported by the software.

Figure 1. Overall Experimental Scheme

Patients will be enrolled when they present to the neurologist for evaluation of stroke or TIA or when they are seen by vascular surgeon for CEA or an interventional cardiologist for carotid stent (**Figure 1**). All patients will have fasting lipid levels, C- Reactive protein and HgBA1C measured as routine standard of care. Symptomatic patients would be required to have plaque $\geq 70\%$ in at least one carotid artery that would be implicated as the source of embolus responsible for the stroke. We propose to enroll 3 patients with stroke or TIA for PET imaging. They will undergo PET-MR of the neck (to image the bilateral carotid arteries) with 18F-Flotegatide within 96h of stroke or TIA and a simultaneous MRI and magnetic resonance angiography (MRA) of the carotid arteries for anatomic localization of the plaque (**Specific Aim 1**). In addition to providing an anatomic map for coregistration of the images obtained by PET, MRI

will provide morphologic information about the carotid plaque. Plaque removed during CEA or carotid stenting in all patients (within 7d of carotid PET-MR) will be used for histologic examination (**Specific Aim 2a**). A small portion of the plaque from 3 symptomatic patients will be used for ex-vivo 18F-flotegatide uptake-competition studies to confirm integrin specific binding (**Specific Aim 2b**). We propose to also enroll 3 asymptomatic patients with a luminal stenosis of $\geq 70\%$ in at least one carotid artery (stable plaque) referred for CEA or carotid stenting. These patients will be age-matched by deciles to symptomatic patients. These patients will undergo PET-MR of the neck (to image the bilateral carotid arteries) with 18F-flotegatide along with an MRI and MRA of their carotid arteries. Plaque removed from asymptomatic patients at the time of CEA or carotid stenting (within 7d of PET-MR) will be used for histologic examination. Exclusion criteria include, stroke due to atrial fibrillation, preexisting carotid stents in the artery of interest, renal dysfunction defined as glomerular filtration rate $<40\text{ml/min}$, allergy to gadolinium based contrast agents, metal implants incompatible with MRI, pregnancy, inability to provide informed consent and age ≤ 18 years. We propose to enroll a total of 6 patients over a period of 1 year.

Section 5.0. Selection of Subjects

Inclusion Criteria:

1. Patients presenting
 - a. to the neurologist for evaluation of stroke or TIA (Symptomatic) with:
 - i. Symptomatic patients with plaque $\geq 70\%$ in at least one carotid artery that would be implicated as the source of embolus responsible for the stroke/TIA.
 - b. or to the vascular surgeon for CEA (Asymptomatic) with:
 - i. asymptomatic patients with a luminal stenosis of $\geq 70\%$ in at least one carotid artery (stable plaque) referred for CEA
 - ii. age-matched by deciles to symptomatic patients
 - c. or to the interventional cardiologist for evaluation and possible carotid stenting with:
 - i. asymptomatic patients with a luminal stenosis of $\geq 50\%$ in at least one carotid artery (stable plaque) referred for carotid stenting
 - ii. age-matched by deciles to symptomatic patients

Exclusion criteria:

1. stroke due to atrial fibrillation,
2. preexisting carotid stents in the artery of interest,
3. renal dysfunction defined as glomerular filtration rate $<40\text{ml/min}$,
4. allergy to gadolinium based contrast agents,
5. Volunteers who have had four or more prior previous gadolinium contrast scans
6. metal implants incompatible with MRI or other condition that prohibits MRI,
7. pregnancy,
8. allergy to animal dander or animal-instigated asthma
9. inability to provide informed consent and
10. age ≤ 18 years.

We propose to enroll a total of 6 patients over a period of 1 year.

Section 6.0**Treatment of Subjects**

All eligible subjects will undergo PET-MR of the neck (to image the bilateral carotid arteries) with 18F-Flotegatide within 96h of stroke or TIA and a simultaneous MRI and magnetic resonance angiography (MRA) of the carotid arteries for anatomic localization of the plaque

Plaque removed from asymptomatic patients at the time of CEA or carotid stenting (within 7d of PET-MR) will be used for histologic examination.

Section 7.0**Assessment of Efficacy**

Validation of the atherosclerotic plaque detected by PET-MRI using 18F-flotegatide will be completed via in-vivo PET imaging of patients with unstable carotid plaque. Plaque will be quantified by measuring the plaque uptake of 18F-flotegatide relative to 18F-flotegatide uptake in segments of the carotid vessel wall that are free of atherosclerosis.

Section 9.0.**Statistics**

Image Analysis of plaque using MRI and MRA: Hemorrhage appears bright on MP-RAGE (**Figure 4**, panel A, yellow arrow). On contrast enhanced T1W images, fibrous portions of atherosclerotic plaque appear bright (**Figure 4** Panel B, arrowhead) and necrotic core in the plaque will be identified on the postcontrast T1W image as the area with no or slight contrast enhancement (**Figure 4** panel B yellow arrow). The percent stenosis will be quantified from TOF images (panel C, bright lumen is shown by the yellow arrow). Thickness of the fibrous cap and volume of lipid rich necrotic core will be quantified and plaque features including hemorrhage, and intact vs ruptured fibrous cap will be recorded.

Image Analysis of PET-MR: PET-MR images will be fused with the simultaneously acquired MR images. Coregistration of PET images with MRI will be performed using anatomic landmarks. Plaque is normally present in the carotid bifurcation and the proximal internal carotid artery. Plaque localized on the axial MR images will be correlated with PET signal. Uptake of 18F-flotegatide will be quantified in regions of interest (ROI) including both the vessel wall and the vessel lumen. The standard uptake value (SUV) in each slice position on the axial images will be quantified as SUVmean and SUVmax using commercially available software (MIM software Inc, Cleveland, OH). These are derived from the injected dose, time to acquisition to account for decay and patient weight. The SUVmax and SUVmean of unaffected segment of the carotid artery as well as the uptake of the tracer in the same level in the contralateral carotid artery will be quantified. SUVmean of the blood pool in the aortic arch will be quantified to derive background uptake. SUVmax of the target ROI is divided by the background SUVmean to derive a target to background ratio (TBR). The TBR of 18F-flotegatide in the plaque will be compared to TBR of unaffected vessel wall.

Comparison of morphologic markers of vulnerability with 18F-flotegatide uptake: MRI based plaque features including, volume of lipid core and thickness of fibrous cap will be directly compared to plaque uptake of 18F-flotegatide expressed as TBR from PET-MR images.

Sample Size and Power for Between Group Comparisons			Sample Size and Power for Correlation		
Effect Size	Number per Group	Power (1-β)	R	Number of Samples	Power (1-β)
1.16	19	80%	0.5	29	80%
1.16	25	90%	0.5	38	90%
1.2	13	80%	0.6	19	80%
1.2	17	90%	0.6	25	90%
1.25	9	80%	0.7	13	80%
1.25	12	90%	0.7	10	90%
1.3	7	80%	0.8	7	80%
1.3	9	90%	0.8	12	90%

Assumes 2-group (Non-paired) design. Level of significance =0.05; Sigma =0.3

For non-parametric Spearman's rank correlation. Level of significance =0.05

Figure 3. Power Calculations

Statistical Analysis

Aim 1.

The statistical analysis is provided to demonstrate how we propose to analyze data when we are able to test our hypothesis in a larger group of patients as part of our future RO1. 18F-flotegatide uptake will be analyzed as a continuous variable. The thickness of fibrous cap and volume of lipid rich necrotic core will also be treated as continuous variables. We will evaluate the use of a parametric test or a transformation of the data (e.g. log transform) prior to using a parametric test. However, if this is not appropriate due to distributional assumptions etc., we will use a nonparametric Mann Whitney U test with the following **null** hypotheses:

1. 18F-flotegatide uptake by carotid plaque (TBR of plaque) in patients with symptoms of stroke or TIA is similar to 18F-flotegatide uptake by the unaffected vessel wall.
2. 18F-flotegatide uptake by carotid plaque (TBR of plaque) implicated in stroke or TIA in symptomatic patients is similar to 18F-flotegatide uptake by stable plaque in asymptomatic patients.
3. There is no correlation between 18F-flotegatide uptake and area of the fibrous cap or volume of necrotic lipid core quantified by MRI.

With a sample size of 17 per group, we will have 90% power to detect a 1.2-fold difference in the TBR of the

plaque responsible for causing stroke/TIA compared to TBR of unaffected vessel wall (based on level of significance of 0.05 and the standard deviation of 0.3 for TBR measurements). For our correlation studies

between TBR of 18F-flotegatide uptake and MRI based characteristics of vulnerability, a sample size of 19 will

provide 80% power to detect at least moderate association (correlation coefficient of 0.6) at a level of significance of 0.05.

The goal of our proposed studies in this R56 application is to demonstrate that detection of 18F-flotegatide by PET-MRI is feasible and that there is a detectable difference in 18F-flotegatide uptake between unstable and stable atherosclerotic plaque. Even though it may not be statistically significant due to the limited number of patients who will be enrolled during the

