Carotid artery containing the plaque (specimen) from 3 symptomatic and 3 asymptomatic patients will be obtained at the time of endarterectomy and labeled with sutures to identify cranio-caudal orientation. The specimen will be divided into three segments (cranial, middle and caudal). This will allow us to identify any particular slice on axial PET images with high 18F-flotegatide uptake (based on SUV_{max}) as located in a specific segment of the specimen. We propose to pick the slice corresponding to the segment (cranial, middle or caudal) with the highest SUV_{max} . This segment of the specimen containing the plaque will be excised and placed in formalin for processing prior to immunohistochemical studies (**Aim 2a. Preliminary Results Figure 8**).

Histological Evaluation of Plaque Composition

Plaque will be placed into 10% Neutral Buffered Formalin for 24 hours after which the samples will be decalcified (Cal-Rite, Richard-Allen Scientific, Kalamazoo, MI). After fixation and decalcification transferred to 70% Ethanol until processing. 5 μ m thick sections will be taken at 1 mm steps. Plaque samples will be processed using the Leica Peloris with a xylene free processing protocol and embedded in paraffin. Sections, 5 microns thick, will be made with a Leica microtome and placed on positively charged slides. Sections will be stained using H&E and Movat's pentachrome staining. H&E staining will identify nuclei (black), calcium (purple), and hemorrhage(magenta) in contrast to the general pink staining of other tissues. The Movat pentachrome can distinguish fibrous regions (dark yellow-green) from lipid rich zones (turquoise). The prior presence of cholesterol appears as "cleft" voids after processing.

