IHC staining will be quantified as the percent area that is stained with the particular antibody for the marker of interest (CD68, macrophage; CD31, neovessel endothelium; α SMA, smooth muscle and Integrin α V β III and α 5 β 1). Percent area of lipid rich necrotic core and fibrous zones will be quantified from Movats staining. Correlation between the TBR of the segment with the highest 18F-flotegatide uptake on PET imaging for each individual patient to the percent area with lipid, fibrous elements, macrophage staining, endothelial staining and smooth muscle staining of the tissue sections from this segment will be evaluated in all patients (**Aim 2. Preliminary Results Figure 8 and 9**). We will also quantify and compare staining in patients with symptoms (unstable plaque) vs asymptomatic patients (stable plaque) (**Aim 2a. Preliminary Results Figure 10**).

Aim 2b.

Ex-vivo Competition Study to Demonstrate Integrin Mediated Binding of 18F-flotegatide
A 5mm segment of plaque from 3 symptomatic patients will be collected for assessment of 18F-flotegatide uptake ex-vivo. This plaque segment will be embedded in optimum cutting temperature compound (Tissue- Plus, Fisher Scientific), snap-frozen in liquid nitrogen and stored at -70°C . Samples will be sectioned using a cryostat (Leica Microsystems, Wetzlar, Germany) and placed on electrically charged glass slides. 20 μm sections will be warmed to room temperature (RT), preincubated for 5 min in PBS buffer, and incubated with 10 nM 18F-flotegatide (specific activity 2.5Ci/ μmol) in PBS buffer for 30 min at RT. Every alternate section from each plaque will be pre-treated with 10 mmol of unlabeled cyclic RGD (Siemens) prior to incubation with 18F- flotegatide. After incubation, the slides will be washed twice for 5 min with PBS, rinsed in cold water, air dried, and placed on an autoradiography imaging plate (Fuji Imaging Plate BAS-MS2040, Fuji Photo Film Co., Ltd., Japan). After overnight exposure, 18F activity in the imaging plates will be measured with Fuji Analyzer FLA- 2000. After co-registration of autoradiography and H&E-stained histological images of the sections, count density (PSL/mm²) of plaques will be quantified. 18F activity (PSL/mm²) in the absence of unlabeled competing tracer will be compared to 18F activity in the presence of competing tracer.

Expected Results

Aim 1.

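### Could reading SUVmax over unequal numbers of slices distort the plaque versus unaffected-wall TBR?

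*Combined protocol and SAP*

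**What the plan says.** Section 9.0, under Image Analysis of PET-MR, sets out the measurement in four steps.

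- Reading: "The standard uptake value (SUV) in each slice position on the axial images will be quantified as SUVmean and SUVmax", in "regions of interest (ROI) including both the vessel wall and the vessel lumen".
- Reference: "The SUVmax and SUVmean of unaffected segment of the carotid artery" are also quantified, together with uptake at the same level of the opposite carotid.
- Ratio: "SUVmax of the target ROI is divided by the background SUVmean to derive a target to background ratio (TBR"). The background is the blood pool of the aortic arch.
- Comparison: "The TBR of 18F-flotegatide in the plaque will be compared to TBR of unaffected vessel wall".

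Section 7.0 names the same contrast, plaque against plaque-free carotid wall, as the efficacy measure, and it is the first expected result of Aim 1. The Experimental Approach for Aim 1 is looser: it allows the opposite carotid or another healthy vessel as the reference.

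A selection rule appears only in Aim 2a. For the specimen: "We propose to pick the slice corresponding to the segment (cranial, middle or caudal) with the highest" SUVmax. For the histology analysis: "Correlation between the TBR of the segment with the highest 18F-flotegatide uptake on PET imaging for each individual patient" is related to staining. Neither is stated for the unaffected wall.

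The PET protocol in Section 4.0 gives the reconstruction, "yielding 512 x 512 image slices (voxel size: 0.70 x 0.70 x 2.03 mm"), and a total of six patients, three symptomatic and three asymptomatic. The Aim 1 statistical text presents the formal analysis as belonging to a later, larger study and expects only qualitative differences here.

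**The concern.** The expected maximum of noisy readings grows with the number of readings, even when the true value is constant. If the plaque is read over many slices and the reference over few, and the highest value is taken on each side, the plaque looks hotter with no extra tracer in it. A longer reference read does the opposite. If one aortic-arch SUVmean per scan is used on both sides, it cancels in the plaque/wall ratio and corrects nothing.

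At stake is the Section 7.0 measure. With three symptomatic patients and no formal test planned, a systematic offset would not show itself. The results are meant as preliminary data for a grant application, and the planning example for that larger study is a 1.2-fold difference in this same contrast. An artefact of several per cent would be a noticeable part of that. The symptomatic versus asymptomatic comparison would be touched only if plaque extent differed between the groups, which the text reviewed does not report.

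**Working it through.** The plan gives no figure for this effect, so there is nothing to reproduce first. The check asks how large the shift could be and under which reading rules it arises.

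**Input from the documents.** Slice thickness 2.03 mm (Section 4.0, PET protocol).

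**Assumed inputs, not in the documents.** Noise CV 5% to 20%; two independent noise elements per slice; reference length 10 mm; plaque read 20 to 40 mm; equal true uptake in plaque and wall.

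**Slice counts.** 10/2.03 = 4.9, taken as 5. 20/2.03 = 9.9, taken as 10. 40/2.03 = 19.7, taken as 20. With two elements per slice these are 10, 20 and 40 readings.

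**Expected maxima of standard normal noise.** 2 readings 0.564; 4 readings 1.029; 10 readings 1.539; 20 readings 1.867; 40 readings 2.161.

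**Spurious ratio.** (1 + CV × plaque maximum) / (1 + CV × reference maximum).

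| Rule and slices (plaque vs reference) | CV 5% | CV 20% |
|---|---|---|
| Hottest slice both sides, 10 vs 5 | 1.0934/1.0769 = 1.015 | 1.3734/1.3078 = 1.050 |
| Hottest slice both sides, 20 vs 5 | 1.1081/1.0769 = 1.029 | 1.4322/1.3078 = 1.095 |
| Hottest slice both sides, 5 vs 20 | 0.972 | 0.913 |
| Hottest slice both sides, equal counts | 1.000 | 1.000 |
| Mean of per-slice maxima both sides, any counts | 1.000 | 1.000 |
| Hottest plaque slice vs mean of reference slices, 5 vs 5 | 1.0769/1.0282 = 1.047 | 1.3078/1.1128 = 1.175 |

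**Correlation between adjacent slices (first-order autoregressive, simulated), 10 to 20 vs 5 slices, CV 5% to 20%.** Correlation 0.8: 1.015 to 1.107. Correlation 0.95: 1.010 to about 1.08. Correlation 0.99: 1.005 to 1.042. Correlation does not always shrink the effect: the upper value at 0.8 is slightly above that for independent noise.

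**A shorter reference.** With one reading per slice and 10 vs 3 slices, the ratio is 1.033 to 1.118 for independent noise, and reaches 1.128 at slice correlation 0.5.

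**Size against the study's precision.** The SD assumed in Section 9.0 is 0.3. With three patients per side, the unpaired standard error of a TBR difference is 0.3 × √(2/3) = 0.245. Take 1.57, the single stable-plaque TBR given with Figure 10, as the uptake level. At CV 20%, 20 vs 5 slices shifts the difference by 1.57 × 0.20 × (2.161 − 1.539) = 0.195, and 10 vs 3 slices by 1.57 × 0.20 × (1.538 − 0.847) = 0.217. Both lie below one unpaired standard error. The mixed rule gives 1.57 × 0.20 × (1.539 − 0.564) = 0.306, which is above it.

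**Which rule the text supports.** One definition of TBR is given. SUVmax is to be measured in the unaffected segment as well as in the plaque, and the two TBRs are compared. The natural reading is the same SUVmax-based summary on both sides. Nothing in the text suggests a hottest slice for plaque against an average for wall, so the 1.175 has little basis in the plan. Under the natural reading, a shift from slice count needs unequal slice counts, which the plan neither prescribes nor excludes.

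**The case for a change.** The strongest case for a change is that few patients excuse the absence of a test but not an undefined measurement. The study is open label, the slices could be chosen after uptake has been seen, and a sentence or two in Section 9.0 would close the gap at almost no cost. The standard-error comparison is also generous to the plan, because plaque and wall are read in the same patient. With a within-patient correlation of 0.5 (assumed), the standard error falls to 0.3 × √(2 × 0.5/3) = 0.173, and the upper-end shifts of 0.195 and 0.217 would exceed it.

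Much of this stands as fact: the rule is not written in the text reviewed, the mechanism is sound and the arithmetic reproduces. It does not show that following the plan gives a wrong answer. Every input that drives the size is assumed except slice thickness, and the result runs from 0.5% to about 13% according to those choices. Nor is averaging per-slice maxima, the obvious firmer rule, a clear gain. It dilutes focal uptake and gives Aim 1 a different TBR from the highest-uptake segment of Aim 2a in the same patients. It also leaves a residual when region areas differ: with double the area per slice, 1.0515/1.0282 = 1.023 at CV 5% and 1.2059/1.1128 = 1.084 at CV 20%, similar in size to the shift removed. The 1.2-fold yardstick belongs to the later study.

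**Conclusion.** The concern does not call for a change. Section 9.0 leaves unwritten how slice values are combined for plaque versus unaffected wall and how long the unaffected segment should be. Part of the preliminary results was not in the text reviewed, so this can be said only of what was available. If maxima were taken over unequal numbers of slices, the ratio could move in either direction: about 0.5% to 11% upward for 10 to 20 slices against 5, up to about 13% for 10 against 3, and down to about 0.90 to 0.91 when the reference is the longer read. These figures assume a noise CV of 5% to 20% and the lengths and correlations listed above; they show what is possible, not what is expected. Equal reads under one rule give a ratio of 1.00.

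The plan already applies one TBR definition to both regions, and whoever draws the regions can match slice counts and outlines as ordinary practice. The looser wording on reference vessels in the Experimental Approach is settled by Sections 7.0 and 9.0, which both name plaque-free carotid wall. For a six-patient feasibility study whose comparisons are descriptive, this is missing detail that analysts fill sensibly. Writing the rule down would be a harmless clarification, and the more specific remedy trades one limitation for another.
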